18.2. DEATHS

If any participants die during the study as recorded on the "Death Details" page of the eCRF, the number and percentage of participants with death related to COVID-19 and those with other deaths will be summarized by actual treatment group based on the SAF. The number and percentage of participants with death related to COVID-19 as adjudicated by the MAC will also be summarized by actual treatment group based on the SAF.

A listing of all deaths will be provided.

18.3. LABORATORY EVALUATIONS

A urine pregnancy test will be performed at screening and per the schedule of events (refer to protocol, Section 1.3). If urine tests positive or indeterminate, a serum test will be performed for confirmation. Chemistry, hematology, coagulation, and urinallysis will be performed as per the schedule of events (refer to protocol, Section 1.3). A list of laboratory parameters to be included in the outputs is included in APPENDIX 3.

Quantitative laboratory parameters reported as "< X", i.e. below the lower limit of quantification (BLQ) or "> X", i.e. above the upper limit of quantification (ULQ), will be converted to X for the purpose of quantitative summaries, but will be presented as recorded, i.e. as "< X" or "> X" in the listings

The following summaries will be provided by actual treatment group based on the SAF for each of chemistry, hematology, coagulation, and urinalysis laboratory parameter:

- Observed and change from baseline in Standard International (SI) units by visit (for quantitative parameters);
- Observed and change from baseline for Illness Visits as defined in Section 6.5 (for coagulation parameters) in
 SI units by Illness Visit (the Illness Visits corresponding to positive RT-PCR test will be used in the summary);
- Number and percentage of participants in each laboratory parameter category by visit (for categorical parameters);
- Shift from baseline to the worst post-baseline observed value according to the Common Terminology Criteria
 for Adverse Events (CTCAE) toxicity grades (for quantitative parameters with available CTCAE toxicity
 grades; refer to Section 18.3.1)
- Shifts from baseline to the maximum/minimum post-baseline observed value according to normal range criteria (for quantitative parameters without CTCAE toxicity grades; refer to Section 18.3.2);
- Maximum post-baseline ALT/AST observed value categorized as < 3 x upper limit of normal (ULN), ≥ 3 to < 5 x ULN, ≥ 5 to < 10 x ULN or ≥ 10 ULN by maximum post-baseline total bilirubin (TBL) observed value categorized as < 2 x ULN or ≥ 2 x ULN

All laboratory evaluations will be listed.

18.3.1. CTCAE TOXICITY GRADES

Quantitative laboratory parameters with available CTCAE toxicity grades will be categorized as follows where higher grades representing a more severe toxicity (refer to APPENDIX 4 for each parameter toxicity grade criteria):

- Grade 1 (i.e., mild);
- Grade 2 (i.e., moderate);
- Grade 3 (i.e., severe)
- Grade 4 (i.e., life-threatening)
- Grade 5 (i.e., death)

Although not defined in the CTCAE toxicity grading system, version 5, non-missing laboratory parameter results not meeting any of the 5 grades defined in the CTCAE toxicity grading system will be categorized as 'No Event' for the purpose of the shift from baseline summaries.

18.3.2. LABORATORY NORMAL RANGES

Quantitative laboratory parameters will be compared with the relevant central laboratory normal ranges in SI units

and categorized as:

- Low: Below the lower limit of the laboratory normal range.
- Normal: Within the laboratory normal range (upper and lower limit included).
- High: Above the upper limit of the laboratory normal range.

18.4. VITAL SIGNS

The following vital sign parameters will be collected for this study as per the schedule of events (refer to protocol, Section 1.3):

- Systolic blood pressure (SBP) (mmHg)
- Diastolic blood pressure (DBP) (mmHg)
- Heart rate (beats per minute [bpm])
- Oxygen saturation (%)
- Respiratory rate (breaths/min)
- Body temperature (°C)

For severity grades of abnormal Vital Signs refer to APPENDIX 5.

The following summaries will be provided by actual treatment group based on the SAF for each vital sign parameter:

- Observed and change from baseline by visit;
- Observed and change from baseline for Illness Visits (as defined in Section 6.5), by Illness Visit (the first illness episode with positive RT-PCR test result will be used for the summary);
- Number and percentages of participants with at least one abnormal post-baseline observed value (refer to APPENDIX 5);

All vital sign data will be listed. Indicators will be included for illness visits to distinguish those with positive RT-PCR results from those with negative RT-PCR results.

18.5. ECG EVALUATIONS

The following electrocardiogram (ECG) parameters will be measured for this study as per the schedule of events (refer to protocol, Section 1.3):

Heart rate (bpm);

- PR interval (msec);
- RR interval (msec);
- QRS interval (msec);
- QT interval (msec);
- QTc interval (msec);
- QTcF interval (msec);
- QTcB interval (msec);
- Overall ECG interpretation (Investigator's judgment):
 - o Normal;
 - o Abnormal, not clinically significant (NCS);
 - o Abnormal, clinically significant (CS)

Since triplicate ECGs will be performed for this study, the mean of the 3 measurements collected on a visit will be used in the by-visit summaries for that visit, but the worst of the 3 measurements collected on a visit will be used for the shift from baseline summaries for that visit. Should one or two of the triplicate measurements be missing at a specific visit, the mean of the available measurements will be used in the by-visit summaries for that visit. All individual measurements will be listed.

The following summaries will be provided by actual treatment group for each ECG parameter:

- Observed and change from baseline by visit (for quantitative parameters);
- Number and percentages of participants with at least one markedly abnormal post-baseline observed value/change from baseline (for quantitative parameters; refer to Section 18.5.1);

All ECG data will be listed.

18.5.1. ECG MARKEDLY ABNORMAL CRITERIA

Markedly abnormal quantitative ECG parameters will be identified in accordance with the following predefined markedly abnormal criteria:

- Observed values for QTc, QTcF, and QTcB intervals will be classified as:
 - o > 450 msec;
 - \circ > 480 msec;

- o > 500 msec
- Change from baseline for QTc, QTcF, and QTcB intervals will be classified as:
 - >30 msec increase from baseline
 - >60 msec increase from baseline

It is to be noted that the previous categories are not mutually exclusive, but cumulative. For example, if a participant's worst post-baseline QTc post-baseline observed value is 490 mmHg, then this participant will be reported once under QTc > 450 msec and once under QTc > 480 msec.

18.6. PHYSICAL EXAMINATION

Physical examinations will be conducted as per the schedule of events (refer to protocol Section 1.3). Clinically significant findings at screening will be recorded on the "Medical History" form of the eCRF while clinically significant changes from screening will be recorded on the "Adverse Events" form of the eCRF for the post-screening visits. Hence, clinically significant findings/changes will be summarized through the Medical history summary (refer to Section 11) or AE summaries (refer to Section 18.1), as appropriate. That is, no summaries will be specifically provided for the general physical examination.

19. OTHER DATA COLLECTED

The following data collected on the eCRF will be summarized in listings only:

- Exposure
- Pregnancy test and report
- Overdose Report
- Medication Error
- Virology: Hepatitis B surface antigen, hepatitis C virus antibody; HIV-I and HIV-II
- Rapid point of care SARS-CoV-2 serology
- Related procedures
- PBMCs for B and T cell responses
- Nasal adsorption for SARS-CoV-2 mucosal responses
- Pharmacogenetics

APPENDIX 1. PARTIAL DATE CONVENTIONS

ALGORITHM FOR PRIOR / CONCOMITANT MEDICATIONS

START DATE	STOP DATE	ACTION
Known Partia Missi	Known or ongoing	If medication stop date < date of dose of IMP, assign as prior; If medication start date < date of dose of IMP and medication stop date ≥ date of dose of IMP, assign as concomitant; If date of dose of IMP ≤ medication start date, assign as concomitant.
	Partial	If known components of medication stop date show that medication stopped before date of dose of IMP, assign as prior; If medication start date < date of dose of IMP and (known components of medication stop date show that medication stopped on or after date of dose of IMP), assign as concomitant; If date of dose of IMP ≤ medication start date, assign as concomitant.
	Missing, not ongoing	If medication stop date is missing, then it can never be assigned as prior only; If medication start date < date of dose of IMP, assign as concomitant; If date of dose of IMP ≤ medication start date, assign as concomitant.
Partial	Known or ongoing	If medication stop date < date of dose of IMP, assign as prior; If (known components of medication start date show that medication started before date of dose of IMP) and (medication stop date ≥ date of dose of IMP), assign as concomitant; If known components of medication start date show that medication started on or after date of dose of IMP, assign as concomitant.

START DATE	STOP DATE	ACTION
	Partial	If known components of medication stop date show that medication stopped before date of dose of IMP, assign as prior; If (known components of medication start date show that medication started before date of dose of IMP) and (known components of medication stop date show that medication stopped on or after date of dose of IMP), assign as
		concomitant; If known components of medication start date show that medication started on or after date of dose of IMP, assign as concomitant.
	Missing, not ongoing	Cannot be assigned as prior only; If known components of medication start date show that medication started before study drug start date, assign as concomitant; If known components of medication start date show that medication started on or after date of dose of IMP, assign as concomitant.
Missing		
	Known or ongoing	If medication stop date < date of dose of IMP, assign as prior; If medication stop date >= date of dose of IMP, assign as concomitant.
	Partial	If known components of medication stop date show that medication stopped before date of dose of IMP, assign as prior; If known components of medication stop date show that medication stopped on or after date of dose of IMP, assign as concomitant.
	Missing, not ongoing	Assign as concomitant.

APPENDIX 2. PROGRAMMING CONVENTIONS FOR OUTPUTS

DATES & TIMES

Depending on data available, dates and times will take the form yyyy-mm-dd hh:mm:ss.

SPELLING FORMAT

English US.

PAPER SIZE, ORIENTATION, AND MARGINS

The size of paper will be letter and the page orientation will be landscape. Margins will provide at least 1 inch (2.54 centimeters) of white space all around the page.

FONTS

The font type 'Courier New' will be used, with a font size of 8. The font color will be black with no bolding, underlining, italics or subscripting.

PRESENTATION OF TREATMENT GROUPS

For outputs, treatment groups will be represented as follows and in the given order:

Treatment Group	Tables and Graphs	Listings
AZD7442	1	1
Placebo	2	2
Total [1]	5	n/a
Randomized, Not Dosed	n/a	3
Screen Failure	n/a	4

^[1] Not applicable for efficacy tables, safety tables and graphs.

PK analyses will be conducted for participants who receive AZD7442 only. Groups will be represented as follows and in the given order:

Treatment Group	Tables and Graphs	Listings
AZD8895	1	1
AZD1061	2	2
AZD7442	3	3

PRESENTATION OF NOMINAL VISITS

For outputs, analysis visits will be represented as follows and in that order:

Long Name (default)	Short Name
Screening	Scrn
Rescreening	RScrn
Day 1	D1
Day 8	D8
Day 29	D29
Day 58	D58
Day 92	D92
Day 183	D183
Day 366	D366
Day 457	D457

For outputs, analysis visits regarding Illness Visit will be represented as follows and in that order:

Long Name (default)	Short Name
Episode 1 Illness Visit Day X,	1IL-DXX,
X=1,3,5,8,11,14,21,28	X=1,3,5,8,11,14,21,28
Episode 2 Illness Visit Day X,	2IL-DXX,

Long Name (default)	Short Name
X=1,3,5,8,11,14,21,28	X=1,3,5,8,11,14,21,28
Episode Y Illness Visit Day X,	YIL-DXX,
X=1,3,5,8,11,14,21,28	X=1,3,5,8,11,14,21,28
Y = 1, 2, 3, and so on, as applicable	Y = 1, 2, 3,

DESCRIPTIVE STATISTICS

If the original data has N decimal places, then the summary statistics will have the following decimal places:

- Minimum and maximum: N;
- Mean, median, Q1, Q3, lower and upper bounds of two-sided 95% CI: N + 1;
- SD and SE: N + 2

PERCENTAGES

Percentages will be reported to one decimal place. Rounding will be applied, except for percentages < 0.1 but > 0.0 which will be presented as '< 0.1' and percentages < 100.0 but > 99.9 which will be presented as '> 99.9'.

Where counts are zero, no percentages will appear in the output.

P-VALUES

p-values will be reported to four decimal places. Rounding will be applied, except for the p-values < 0.0001 which will be presented as < 0.0001' and p-values < 1.000 but > 0.9999 which will be presented as < 0.9999'.

LISTINGS

All listings will be ordered by the following (unless otherwise indicated in the output template):

- Randomized treatment group (or treatment received if it's a safety output);
- Participant ID;
- Parameter, when applicable;
- Date/Time, when applicable;
- Timepoint, when applicable

APPENDIX 3. LABORATORY ASSESSMENTS

Ch	emistry (SI unit)		
•	Alkaline phosphatase (ALP) (U/L)	•	Creatinine (µmol/L)
•	Alanine transaminase (ALT) (U/L)	•	Glucose (mmol/L)
•	Aspartate transaminase (AST) (U/L)	•	Creatine kinase (CK) (U/L)
•	Total bilirubin (µmol/L)	•	Sodium (mmol/L)
•	Conjugated bilirubin (µmol/L)	•	Potassium (mmol/L)
•	Gamma glutamyl transferase (GGT) (U/L)	•	Calcium (mmol/L)
•	C-Reactive protein (CRP) (nmol/L)	•	Phosphate (mmol/L)
•	Albumin (g/L)	•	Urea (mmol/L)
Не	matology (SI unit)		
•	Hemoglobin (g/L)	•	Absolute neutrophils count (x10E9/L)
•	Hematocrit	•	Absolute lymphocyte count (x10E9/L)
•	Mean corpuscular volume (MCV) (fL)	•	Absolute monocyte count (x10E9/L)
•	Red blood cells (RBC) count total (x10E12/L)	•	Absolute eosinophils count (x10E9/L)
•	White blood cell (WBC) count total (x10E9/L)	•	Absolute basophils count (x10E9/L)
•	Mean corpuscular hemoglobin (MCH) (pg)	•	Absolute reticulocyte count (x10E9/L)
•	Mean corpuscular hemoglobin concentration (MCHC) (g/L)	•	Platelet count (x10E9/L)

Coagulation (SI unit)	
International normalized ratio (INR)	• Prothrombin time (PT) (s)
• Activated partial thrombin time (aPTT) (s)	
Urinalysis (SI unit)	
Dip stick	Microscopy
• Blood	White blood cells
• Protein	Red blood cells
• Glucose	• Casts

		baseline	> baseline - <	$> 1.5 - \le 3.0 \text{ x}$	baseline if	baseline if	
		abnormal	1.5 x baseline	baseline if	baseline	baseline	
			if baseline	baseline	abnormal	abnormal	
			abnormal	abnormal			
Gamma glutamyl	GGT (U/L)	≥ ULN if	> ULN -	> 2.5 –	$> 5.0 - \le 20.0 \text{ x}$	> 20.0 x ULN if	n/a
transferase (GGT)		baseline	≤ 2.5x ULN if	$\leq 5.0 \text{ x ULN if}$	ULN if baseline	baseline	
increased		normal;	baseline	baseline	normal;	normal;	
		$\leq 2.0 \text{ x}$	normal;	normal;	$> 5.0 - \le 20.0 \text{ x}$	> 20.0 x	
		baseline if	> 2.0 -	> 2.5 -	baseline if	baseline if	
		baseline	\leq 2.5 x baseline	\leq 5.0 x baseline	baseline	baseline	
		abnormal	if baseline	if baseline	abnormal	abnormal	
			abnormal	abnormal			

STATISTICAL ANALYSIS PLAN D8850C00002 – ed. V4.0

AstraZeneca 29-Jul-2021

CTCAE Term	Laboratory Test	No Event	Grade 1	Grade 2	Grade 3	Grade 4	Grade 5
Hypoalbuminemia	Albumin (g/L)	> LLN	≥ 30 g/L - < LLN	> 20 - < 30 g/L < 20 g/L	< 20 g/L	n/a	n/a
CPK increased	Creatine kinase (U/L)	≥ ULN	> ULN - ≤ 2.5 x ULN	> 2.5 – ≤ 5 x ULN	> 5 - ≤ 10 x ULN	> 10 x ULN	n/a
International normalized ratio (INR) increased	INR	<pre><!--.2 if not on anticoagulant; </pre--> <pre><pre><pre></pre> <pre><pre><pre><pre><pre><pre><pre><pre></pre></pre></pre></pre></pre></pre></pre></pre></pre></pre></pre>	> 1.2 – ≤1.5 if not on anticoagulant; > baseline - ≤1.5 x baseline if on anticoagulant	> 1.5 – \le 2.5 if not on anticoagulant; > 1.5 - \le 2.5 x baseline if on anticoagulant	> 2.5 if not on anticoagulant; > 2.5 x baseline if on anticoagulant	n/a	n/a

APPENDIX 5. CLINICAL ABNORMALITIES: VITAL SIGNS

	Vital Signs Grade			
Vital Signs ^a	Mild (Grade 1)	Moderate (Grade 2)	Severe (Grade 3)	Potentially Life Threatening (Grade 4)
Fever (°C) ^b (°F) ^b	37.9-38.4 100.1-101.1	38.5-38.9 101.2-102.0	39.0-40 102.1-104	> 40 > 104
Tachycardia (beats/minute)	101-115	116- 130	> 130	ER visit or hospitalization for arrhythmia
Bradycardia (beats/minute) ^c	50-54	45-49	< 45	ER visit or hospitalization for arrhythmia
Hypertension; systolic (mm Hg)	141-150	151-155	> 155	ER visit or hospitalization for malignant hypertension
Hypertension; diastolic (mm Hg)	91-95	96-100	> 100	ER visit or hospitalization for malignant hypertension
Hypotension; systolic (mm Hg)	85-89	80-84	< 80	ER visit or hospitalization for hypotensive shock
Respiratory rate (breaths/minute)	17-20	21-25	> 25	Intubation

Note: Record vital signs as adverse events only if clinically relevant and changed from baseline.

ER = emergency room; Hg = mercury.

^a Participant should be at rest for vital signs measurements.

^a No recent hot or cold beverages or smoking.

^b Use clinical judgment when characterizing bradycardia among some healthy participant populations, for example, conditioned athletes.

APPENDIX 6. HIGH RISK OF SEVERE COVID-19 AT BASELINE

High Risk of Severe COVID-19 Condition	Description	
History of Obesity: (eCRF)	COVID Co-Morbidities eCRF: "Does the subject have a history of Obesity those with a BMI greater than 30"	
	Programming example: MHDIAGYN4 = "Y"	
Obese: BMI ≥30 (derived)	Derived from the participant's reported height and weight at baseline	
Morbid Obesity: BMI ≥40 (derived)	Derived from the participant's reported height and weight at baseline	
CKD	COVID Co-Morbidities eCRF: "Does the subject have a history of Chronic kidney disease?"	
	Programming example: MHDIAGYN1 = "Y"	
Diabetes	COVID Co-Morbidities eCRF: "Does the subject have a history of Type 1 diabetes?"	
	"Does the subject have a history of Type 2 diabetes?" Programming example: MHDIAGYN15 = "Y" or MHDIAGYN7 = "Y"	
Immunosuppressive	From reported Medical History Term	
disease	Programming example: SOC_NAME = "IMMUNE SYSTEM DISORDERS" and HLGT different than 'ALLERGIC CONDITIONS'	
Immunosuppressive treatment	From reported Concomitant medications identified as prior and ongoing with ATC2 is 'L01' or 'L04'.	
CV disease	COVID Co-Morbidities eCRF: "Does the subject have a history of Serious heart conditions like heart failure and coronary artery disease"	
	Programming example: MHDIAGYN5 = "Y"	
COPD	COVID Co-Morbidities eCRF: "Does the subject have a history of Chronic obstructive pulmonary disease (COPD), like emphysema?" Programming example: MHDIAGYN2 = "Y"	
Chronic liver disease	COVID Co-Morbidities eCRF: "Does the subject have a history of Liver disease?"	
	Programming example: MHDIAGYN13 = "Y"	
Hypertension	COVID Co-Morbidities eCRF: "Does the subject have a history of High blood pressure?"	
	Programming example: MHDIAGYN12 = "Y"	
Asthma	COVID Co-Morbidities eCRF: "Does the subject have a history of Asthma?"	
	Programming example: MHDIAGYN8 = "Y"	
Cancer	From ongoing Medical History terms where SOC NAME='NEOPLASMS BENIGN, MALIGNANT AND UNSPECIFIED (INCL CYSTS AND POLYPS)' and PT name different than 'UTERINE LEIOMYOMA'	
Smoking	COVID Co-Morbidities eCRF: "What is the subject's smoking history?" MHDIAGYN17 = "1" ("Current smoker")	

High Risk of Severe	
COVID-19 Condition	Description
Sickle cell disease	COVID Co-Morbidities eCRF: "Does the subject have a history of Sickle cell disease?"
	Programming example: MHDIAGYN6 = "Y"

Note: Final programming logic may differ to address the specific data elements such as additional fields, different field name, or levels.

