5.1 Inclusion Criteria

Participants are eligible to be included in the sub-study if all the following criteria apply:

- 1 The participant has been randomized, dosed, and is ongoing in the PROVENT parent study and is 12 ± 2 months post first dose of blinded IMP.
- 2 If one or more of the following apply:
 - (a) Immunocompromised and/or may be at increased risk for an inadequate immune response to a COVID-19 vaccine, including:
 - o Elderly, ie, \geq 60 years old
 - Obese, ie, Body Mass Index≥ 30
 - Congestive heart failure
 - Chronic lung disease
 - Chronic kidney disease, ie, GFR < 30 mL/min/1.73 m² (Lamb et al 2013)
 - Chronic liver disease
 - Immunocompromised state from solid organ transplant, blood or bone marrow transplant, immune deficiencies, human immunodeficiency virus, use of corticosteroids, or use of other immunosuppressive medicines
 - Intolerant of vaccine. Defined as previous history of severe AE or SAE after receiving any approved vaccine.
 - (b) In the opinion of the Investigator, are at increased risk and would benefit from a repeat dose of AZD7442 (eg, participants who have a chronic condition that increases

their risk of severe COVID-19 or those who have not been vaccinated against COVID-19).

- Medically stable defined as disease not requiring significant change in therapy or hospitalization for worsening disease during the one month prior to enrollment to the substudy, with no acute change in condition at the time of sub-study enrollment as judged by the Investigator. This includes conditions newly diagnosed since the participant entered the parent study.
- 4 Documented negative SARS-CoV-2 RT-PCR test collected ≤ 3 days prior to SS-D1 or a negative rapid SARS-CoV-2 antigen test at screening.

Reproduction

- 5 Contraceptive use by men or women:
 - (a) Male Participants: Contraception for male participants is not required, however, to avoid the transfer of any fluids, all male participants must use a condom from SS-D1 and agree to continue through 365 days following administration of the IMP.
 - (b) Female Participants:
 - Women not of childbearing potential are defined as women who are either permanently sterilized (hysterectomy, bilateral oophorectomy, or bilateral salpingectomy), or who are postmenopausal. Women will be considered postmenopausal if they have been amenorrhoeic for 12 months prior to the planned date of randomization without an alternative medical cause. The following age-specific requirements apply:

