7.7. EXAMINATION OF SUBGROUPS

Subgroup analyses will be conducted as stated in Section 16.1.7. It should be noted that the study was not designed to detect treatment differences with high statistical power within subgroups.

The list of subgroups includes but may not be limited to:

- Categorical age (years) at informed consent (3 groupings 1: ≥60 years and <60 years, 2: ≥65 years and <65 years, 3: ≥75 years and <75 years);
- Residence in long-term care facility (yes and no);
- Increased risk of exposure to infection with SARS-CoV-2 (yes and no);
- Increased risk for inadequate response to active immunization (yes and no);
- Sex (male and female);
- Region (North America, United Kingdom, and European Union);
- Country (United States, United Kingdom, Belgium, France, Spain);
- Race (American Indian or Alaska Native, Asian, Black or African American, Native Hawaiian or Other Pacific Islanders, White);
- Ethnicity (Hispanic or Latino, Not Hispanic or Latino);
- COVID-19 co-morbidities at baseline (at least one co-morbidity, no co-morbidity);
- High Risk for severe COVID-19 at baseline (History of Obesity, Obese (baseline BMI≥30), Morbid Obesity (baseline BMI≥40), Chronic kidney disease (CKD), Diabetes, Immunosuppressive disease, Immunosuppressive treatment, Cardiovascular disease (CV disease), Chronic obstructive pulmonary disease (COPD), Chronic liver disease, Hypertension, Asthma, Cancer, Smoking, Sickle cell disease) (yes/no; refer to APPENDIX 1 for description of each condition).

If models of subgroup analysis do not converge due to sparse data, changes to planned subgroup analysis will be described in the CSR.

Subgroup data will be obtained from the EDC system for items collected in both EDC and Interactive Response Technology (IRT).

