16.1.7. SUBGROUP ANALYSES FOR PRIMARY EFFICACY ENDPOINT

Subgroup analysis will be performed for the primary efficacy endpoint, SARS-CoV-2 RT-PCR-positive symptomatic illness occurring post dose of IMP and prior to Day 183. For subgroup analysis, FPAS will be used. Treatment-by-subgroup interaction will be tested using the Poisson regression with robust variance model adjusting for follow-up time with the terms of planned treatment, age group (Section 7.6), subgroup, and treatment-by-subgroup interaction, which will be implemented using PROC GENMOD procedure. If this full model does not achieve convergence, a reduced model of planned treatment, subgroup, and treatment-by-subgroup interaction will be considered. Within each level of a subgroup, the RRR and its corresponding 95% CI will be estimated using a Poisson regression model with robust variance with the term of treatment. A forest plot of the RRR and the 95% CI will be presented. If the CMH model is used for primary analysis (e.g. if the Poisson regression model fails to converge), a CMH model will also be used for subgroup analyses to generate the RRR and the corresponding 95% CI.

The subgroup analysis will be conducted for the subgroups in Section 7.7 on the FPAS population.

For subgroups corresponding to one of the factor levels included in the analysis model, the corresponding factor will not be included in the model. For example, the age group factor will not be included in the model for the analysis of participants ≤ 60 years old at the time of informed consent subgroup and analysis of participants ≥ 60 years old at

the time of informed consent subgroup.

No adjustment to the significance level for testing of all these subgroup analyses will be made since all these analyses will be considered supportive of the primary analysis.

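### The SAP's 'Cancer' flag is built from all ongoing neoplasm terms, benign ones included, so the subgroup and baseline row can contain participants with no malignancy

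*SAP*

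**What the plan says.** SAP 7.7 lists "High Risk for severe COVID-19 at baseline" among the subgroup factors and names the component conditions, Cancer among them, each as yes/no. SAP 16.1.7 specifies, for each subgroup, a treatment-by-subgroup interaction test, a relative risk reduction with 95% CI within each level, and a forest plot. SAP 10 reports the same conditions as baseline characteristics.

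The derivation is in SAP Appendix 6. The Cancer row starts "From ongoing Medical History terms where SOC NAME" and the condition is "SOC NAME='NEOPLASMS BENIGN, MALIGNANT AND UNSPECIFIED (INCL CYSTS AND POLYPS)' and PT name different than 'UTERINE LEIOMYOMA". It gives no further filter by malignancy, either at a group level of the dictionary or through a reviewed term list. Several other rows mark their logic as a programming example; the Cancer row does not. The table closes with a caveat: "Note: Final programming logic may differ to address the specific data elements such as additional fields, different field name, or levels".

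**The concern.** The label says cancer, but the rule says any neoplasm other than uterine leiomyoma. The class's own name states that it is not confined to malignancy. A participant whose only ongoing term in that class is benign is therefore tabulated and analysed as having cancer.

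Two outputs are affected. The baseline table would report a number with cancer that includes people without it. The forest plot would carry a row that readers take as evidence on protection in patients with cancer, a group in which a reduced effect is plausible and the result will be looked at. Any true difference would be diluted in that row and in its interaction test.

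**Working it through.** **Step 1: is the breadth deliberate?** The one exclusion shows that the authors recognised a benign tumour as out of place under this heading, but the rule removes only that term. In the same table, the immunosuppressive disease row filters below class level ("and HLGT different than 'ALLERGIC CONDITIONS"), so a finer filter was available. The closing caveat concerns fields, field names and levels; it does not commit to removing benign terms. The rule as written is broader than its label.

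**Step 2: is there a figure to reproduce?** No. Neither document gives the number flagged, the prevalence of cancer, or a benign/malignant split. What follows is illustration only.

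**Step 3: dilution.** Let *b* be the share of flagged participants with no malignancy (assumed), *e_c* the efficacy in people with cancer (assumed), and *e_n* the efficacy in people without, set to 80%, the design assumption in SAP 7.1. With equal placebo risk in the two parts:

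flagged-group efficacy = 1 − [(1 − b)(1 − e_c) + b(1 − e_n)]

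| b | 0% | 10% | 25% | 50% | 75% | 90% |
|---|---|---|---|---|---|---|
| e_c = 80% | 80% | 80% | 80% | 80% | 80% | 80% |
| e_c = 50% | 50% | 53% | 57.5% | 65% | 72.5% | 77% |
| e_c = 20% | 20% | 26% | 35% | 50% | 65% | 74% |

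Worked cell, e_c = 50% and b = 50%: 1 − [0.5 × 0.5 + 0.5 × 0.2] = 1 − 0.35 = 65%.

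The interaction shrinks with it. The ratio of relative risks, flagged to unflagged, is 0.50/0.20 = 2.5 at b = 0 and 0.35/0.20 = 1.75 at b = 50%.

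**Step 4: precision.** SAP 4.4 plans the primary analysis at about 24 events. If 5% to 20% of events fell in the flagged group (assumed), that is 24 × 0.05 = 1.2 to 24 × 0.20 = 4.8 events. The subgroup interval would be very wide under either definition.

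**Step 5: related text.** Two nearby statements also need tidying.
- SAP 11 defines medical history as conditions that had ended before dosing, and SAP 12 treats ongoing conditions as concomitant illnesses. A flag built on ongoing medical history therefore needs its source data named.
- SAP 7.7 sends the reader to the wrong place ("Chronic liver disease, Hypertension, Asthma, Cancer, Smoking, Sickle cell disease) (yes/no; refer to APPENDIX 1 for description of each condition"). Appendix 1 covers partial dates; the condition descriptions are in Appendix 6.

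**The case against.** The strongest reply is that this is a labelling matter in one of many unadjusted flags. SAP 7.7 warns of limited power within subgroups, and 16.1.7 says that "all these analyses will be considered supportive of the primary analysis". With a handful of events, 50% and 65% could not be told apart. If efficacy is the same in both parts, there is no bias in the estimate. SAP 11 and 12 also tabulate the underlying terms by class and preferred term, so a careful reader could see what feeds the flag. And Protocol 2.3.2 reports the parent study's primary analysis as done, with 25 cases, so nothing can now be fixed ahead of it.

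Most of that stands and limits the weight of the point. It does not remove it. The baseline count is mislabelled whatever the power, and the final analysis under SAP 4.5 can still use a corrected flag.

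Three stronger readings are tempting, and the documents do not support them.
- A reader might infer that the subgroup mostly describes people without cancer. That needs b above 50%, and nothing in either document gives or implies a value. Nor can it be said which particular lesions would be flagged, since that depends on dictionary coding that is not reproduced.
- A reader might infer that the table overstates how many participants with a history of cancer were studied. The rule counts only ongoing terms, so resolved malignancies drop out, and the net direction is unknown.
- A reader might extend the criticism to the immunosuppressive disease row, comparing it with the immunocompromised states in Protocol 5.1. That row's class rule is only a programming example. The comparison list belongs to the later repeat-dose addendum, whereas this SAP serves the placebo-controlled parent study. Immunosuppressive treatment also has its own row.

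**Conclusion.** The point holds as a definitional error of limited reach. As written, the Cancer flag admits every ongoing neoplasm term but one, so the subgroup and the baseline row can include an unknown number of participants with no malignancy. The count does not mean what its label says. If efficacy differs in cancer, the subgroup estimate moves toward that of people without cancer.

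The size is not known. The table of illustrative values rests wholly on assumed mixes, assumed efficacy in cancer and equal placebo risk. The primary efficacy result is untouched. So is the repeat-dose sub-study, which tests no hypotheses, is summarised descriptively by cohort, and does not use this flag. The change is still worth making because the rule is wrong on its face and cheap to correct.

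**What to change.** Replace the Cancer row in SAP Appendix 6 with a malignant-only MedDRA term list. Have it medically reviewed by people without access to treatment assignment or outcome, and let that review settle how unspecified neoplasm terms are handled. Apply the list to all remaining parent-study reporting, including the final analysis. Disclose it as a change made after the primary analysis. If no list is produced, the minimum is to relabel the row *Neoplasm, any (including benign)* in the baseline table and forest plot.

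In the same edit, name the data source for ongoing conditions and point SAP 7.7 to Appendix 6.

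The cost is an appendix edit and one review of coded terms. The downside is a smaller Cancer subgroup with a wider interval.
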